8.6 Vital Signs

Vital signs (pulse rate, blood pressure, respiration rate, and temperature) will be measured at Screening, during the Treatment Visits, and Follow-Up as specified in the [Schedule of Assessments](#).

Blood pressure and heart rate will be measured using a calibrated, fully automated machine with a cuff that is appropriate to the size of the upper arm. If a fully automated machine is not available, blood pressure may be measured manually. Blood pressure at the Screening Visit should be obtained in both arms and the arm with the higher value should be used for ongoing monitoring throughout the rest of the study. For each subject, measurement on the same arm (right or left) using the same method (either automated or manual) should occur throughout the study. All blood pressure measurements should be obtained with the subject in the sitting position, after the subject is at rest for 5 minutes.

For purposes of qualifying any given subject for study participation based on Inclusion/Exclusion Criteria, out-of-range results may be repeated once at Screening and once at

Baseline. Eligibility must be confirmed at Baseline. Additional vital signs measurements may be performed as deemed medically necessary by the Investigator.

8.7 Electrocardiograms

Single 12-lead ECGs will be performed at every clinic visit except the Week 14 Follow-up Visit, as Visit as specified in the Schedule of Assessments.

ECGs should be obtained after the subject has been resting comfortably in a supine position for approximately 5 minutes. ECGs will be collected prior to blood collection whenever possible.

ECGs will be assessed locally for eligibility determinations and safety, and electronic tracings will also be sent to a central reader for review. All ECG traces will be kept as source data.

For purposes of qualifying any given subject for study participation based on Inclusion/Exclusion Criteria, the ECG may be repeated once in the case of clinically significant out-of-range results. The ECG may be repeated immediately or later within the visit.

8.8 Laboratory Assessments

Appendix 16.2 [Clinical Laboratory Analytes](#) provides a list of the clinical laboratory tests that will be performed according to the collection schedule provided in the [Schedule of Assessments](#).

Blood samples for chemistry, hematology and lipid testing and urine samples will be collected in accordance with acceptable laboratory procedures. Blood samples for chemistry, hematology and lipid testing performed on Day 1 and Week 13 require an 8 hour fast and will include glucose testing; samples obtained at all other visits do not require fasting and will not include glucose or lipid testing.

A central laboratory will be used to analyze the clinical laboratory samples.

8.9 Management of Abnormal Clinical Laboratory Tests

It is the Investigator's responsibility to review the results of all lab tests as they become available and to document their review by signing and dating the lab report. For each lab test outside of the laboratory normal range, the Investigator must ascertain if this is a clinically significant change from baseline for the individual subject. This determination does not necessarily need to be made the first time an abnormal lab is observed. The Investigator may repeat the lab test or request additional tests to verify the results of the original lab test.

All clinically significant laboratory abnormalities occurring during the study that were not present at baseline should be reported as AEs, and followed and evaluated with additional tests if necessary until determination of the underlying cause or adverse event resolution.

8.10 Columbia Suicide Severity Rating Scale (C-SSRS)

The Columbia Suicide Severity Rating Scale (C-SSRS) is a prospective assessment instrument that directly classifies suicidal ideation and behavior into 11 preferred categories.⁸ The C-SSRS involves a series of probing questions to inquire about possible suicidal thinking and behavior.

The C-SSRS will be conducted Screening, Baseline, Week 1 and Week 4, as specified in the Schedule of Assessments.

At Screening, a subject is ineligible for the study if the subject scores a suicidal ideation intensity of 3 or higher (per the C-SSRS) or has exhibited any suicidal behavior within the past three months.

If a subject scores an intensity of 3 or higher for suicidal ideation (per the C-SSRS) during the Treatment and Follow-Up Visits a suicide risk assessment must be completed by the investigator. If a subject scores an intensity of 3 or higher for suicidal ideation and has any suicidal behavior, the subject will be discontinued from the study and referred for psychiatric evaluation.

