Note: Other prescription or non-prescription drugs necessary for the patient's welfare, such as antihypertensive or cholesterol lowering agents are allowed, if, in the Investigator's judgement, they would not interfere with the study medication or the cognitive testing.

17. A suicidal ideation intensity score of 3 or higher per screening Columbia Suicide Severity Rating Scale (C-SSRS) assessment on Day 1 (Baseline) and/or any suicidal behavior within the past 3 months.
18. History of chronic alcohol or other substance abuse, including marijuana, within the previous year prior to the Screening visit (per the current edition of the Diagnostic and Statistical Manual of Mental Disorders, 5th Edition: DSM-5), or regular (daily) consumption of alcohol exceeding two bottles of beer, or the equivalent amount of other forms of alcohol (1 serving = 12 oz beer, 5.0 oz wine, or 1.5 oz distilled spirits).
19. Inability or unwillingness to comply with the protocol, including performing the cognitive function tests, or likely inability to complete the study.
20. Participation in other clinical studies involving investigational drug within the previous 30 days prior to the Screening Visit. Participation in other clinical trials of monoclonal antibody products requires a 90-day wash out period prior to the Screening Visit.
21. Donation of blood within 4 weeks, or blood products within 2 weeks, prior to first study drug administration.
22. History of clinically significant drug allergy that includes symptoms such as shortness of breath, rash, or edema.
23. Clinically significant B12 deficiency based on clinical diagnosis within 12 months prior to Screening. Participants on stable replacement therapy for a minimum of 3 consecutive months immediately prior to Screening may be included.

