6.4 Subject Withdrawal

All subjects have the right to withdraw from this study at any time. In addition, it is the right of the Investigator to remove subjects from the study as a result of adverse reactions, a protocol violation, or non-compliance, or any other reason. Subjects must be discontinued for the following reasons:

- Subject withdraws consent or requests discontinuation from the study for any reason;
- Occurrence of a medical condition or circumstance that exposes the subject to substantial risk and/or does not allow the subject to adhere to the requirements of the protocol as determined by the Investigator;
- Any serious adverse event (SAE), clinical significant adverse event, severe laboratory abnormality, concomitant illness, or other medical condition which indicates to the Investigator that continued participation is not in the best interest of the subject;
- Pregnancy;
- Requirement for prohibited concomitant medication;
- Termination of the study by the Sponsor or the regulatory authority.

Should a subject withdraw after administration of BPN14770 (or placebo), or should the Investigator decide to withdraw the subject, all efforts will be made to complete and report the protocol-stipulated observations up to the time of withdrawal. Week 13 procedures (see Section 10.3 Week 13) and [Section 16.1 Schedule of Study Assessments](#)) will be completed at the time of the subject's withdrawal and an explanation provided as to why the subject is withdrawing or being withdrawn from the study.

In a case of subjects lost to follow-up, attempts to contact the subject must be made and documented in the subject's medical records.

The Investigator must document the primary reason for discontinuation of a study subject on the appropriate case report form (CRF). If the reason for withdrawal is a clinical AE, monitoring will continue until the AE resolves or the Investigator assesses the AE as chronic and stabilized.

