8.11 Additional Safety Measures

Subjects and caregivers will be instructed to inform the study physician and/or research personnel of any AEs that occur at any time during the study.

Procedures will be completed as specified in this protocol unless contraindicated due to a reported AE.

If, in the judgement of the Investigator, additional testing is required to assess an adverse event or otherwise clinically significant event, this testing should be discussed first with the sponsor unless needed urgently.

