9.3.3 Adverse Event Monitoring and Follow-up

Subjects who experience AEs will be monitored with relevant clinical assessments and laboratory tests, as determined by the Investigator. In accordance with good medical practice, all AEs must be followed to satisfactory resolution or stabilization of the event(s), or, if a chronic condition, until fully characterized. All follow-up results are to be reported to the Sponsor. Any actions taken and follow-up results must be recorded either on the appropriate page of the CRF or in a follow-up letter to the Sponsor, as well as in the subject's source documentation. Follow-up laboratory results should be filed with the subject's source documentation.

For all AEs that require the subject to be discontinued from the study, relevant clinical assessments and laboratory tests must be repeated at appropriate intervals until final resolution or stabilization of the event(s).

Subjects who have non-serious AEs that are ongoing at study completion or study withdrawal must be followed until resolution of the AEs or for 30 days after the last dose of study drug, whichever comes first. Subjects who have an ongoing SAE at study completion or study withdrawal must be followed until the event resolves or the event or sequela stabilizes.

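### Both on-study C-SSRS actions in Protocol 8.10 require ideation of 3 or higher, so suicidal behavior with lower ideation triggers neither, although behavior alone excludes at entry

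*Protocol*

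**What the plan says.** Protocol 8.10 has one entry rule and two on-study rules.

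- **Entry, at Screening.** A subject is ineligible with ideation intensity of 3 or higher "or has exhibited any suicidal behavior within the past three months". Exclusion 17 (Protocol 6.3 and the synopsis) agrees, joining its two conditions by "and/or any suicidal behavior within the past 3 months".
- **On study, risk assessment.** The trigger is "If a subject scores an intensity of 3 or higher for suicidal ideation (per the C-SSRS) during the Treatment and Follow-Up Visits"; the investigator must then complete a suicide risk assessment.
- **On study, discontinuation and psychiatric referral.** These follow when a subject "scores an intensity of 3 or higher for suicidal ideation and has any suicidal behavior, the subject will be discontinued from the study".

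The schedules in Protocol 16.1 and SAP 3.7 place on-treatment C-SSRS assessments at Weeks 1, 4 and 13. SAP 11.8 defines suicidal ideation (Categories 1 to 5) and suicidal behavior (Categories 6 to 10) as separate endpoints. SAP Table 4 places a subject who has both under behavior.

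**The concern.** The on-study rules make the response to behavior depend on the ideation score. A subject with ideation of 3 and no act must have a risk assessment. Under the same section, a subject who makes an attempt but is scored below 3 on ideation requires no assessment and no referral. The entry rules and the SAP tabulation both let behavior count on its own, so the on-study rule is out of line with the rest of the plan.

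What is at stake is subject safety. For a subject in this position, both protective steps depend on the investigator choosing to take them. No effect on the efficacy endpoints or their analysis is claimed.

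**Working it through.** The plan states no figure here to reproduce. The check is a reading of the rules as a two-by-two table, followed by a rough sense of scale.

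**Step 1. The rules in 8.10 by ideation and behavior.**

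| Ideation | Any suicidal behavior | At entry | On study |
|---|---|---|---|
| 3 or higher | Yes | Excluded | Risk assessment, discontinuation, referral |
| 3 or higher | No | Excluded | Risk assessment |
| Below 3 | Yes | Excluded | No action |
| Below 3 | No | Eligible on this criterion | No action |

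The third row is the gap. It is the only row that excludes at entry but calls for no action on study.

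**Step 2. Can the third row be recorded?** Yes. SAP 11.8 scores behavior separately from ideation. It also states that on-treatment answers cover the time since the prior visit, and the scheduled assessments jump from Week 4 to Week 13. Subjects are enrolled with impaired delayed memory (RBANS DMI of 85 or below, Protocol 6.2). An act could therefore come to light, for example through a caregiver, when the ideation the subject recalls scores low. This is an inference, not a documented rate.

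**Step 3. Do other sections supply the missing steps?**

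- Protocol 6.4 makes withdrawal mandatory for "Occurrence of a medical condition or circumstance that exposes the subject to substantial risk", as determined by the investigator, or for an SAE or clinically significant AE "which indicates to the Investigator that continued participation is not in the best interest of the subject". It does not name suicidality and requires neither a risk assessment nor a referral.
- Protocol 8.11 opens with "If, in the judgement of the Investigator, additional testing is required to assess an adverse event or otherwise clinically significant event". The choice is the investigator's.
- Protocol 9.3.3 is mandatory for AEs but leaves the content open: "Subjects who experience AEs will be monitored with relevant clinical assessments and laboratory tests, as determined by the Investigator".
- Protocol 9.3.4 requires reporting within 24 hours if the event is an SAE. That is a reporting duty, not a clinical response.

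None of these requires a suicide risk assessment or psychiatric referral for behavior alone.

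**Step 4. Scale.** The rule governs 3 scheduled on-treatment assessments in 255 planned subjects: 3 × 255 = 765 at most. That is how often the rule is applied, not how often the gap occurs. The documents give no rate for behavior with ideation below 3. Taking an assumed per-subject rate p over the study, the expected number is 255p and the chance of at least one is 1 − (1 − p)^255:

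| Assumed p | Expected subjects | Chance of at least one |
|---|---|---|
| 0.1% | 0.255 | 1 − 0.999^255 = 0.225 |
| 0.5% | 1.275 | 1 − 0.995^255 = 0.721 |
| 1% | 2.55 | 1 − 0.99^255 = 0.923 |

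The width of the last column reflects only the tenfold range assumed for p. Exclusions 4 and 17 should push p down.

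**The case against.** The strongest reply accepts the logic and disputes the weight.

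- **The cell is narrow.** SAP 11.8 lists self-injury without suicidal intent separately, so Categories 6 to 10 imply some intent. Ideation with some intent is already Category 4. An attempt within the recall window would then usually come with ideation of 3 or higher and trigger both actions. This is reasonable as an expectation, and it is why few subjects are likely to be affected. It does not cover impulsive acts or poor recall, and a safety rule should not rely on the two scores moving together.
- **The backstops are stronger than they look.** AE follow-up under 9.3.3 is compulsory. An attempt would often meet the SAE definition in 9.2.3, bringing prompt IRB notice (13.2), and the DSMB reviews safety data (9.4). Protocol 8.10 does not define the content of its own risk assessment either. All of this stands as mitigation. None of it produces a mandatory suicide risk assessment or a referral, and for preparatory acts or aborted attempts the SAE classification may itself turn on medical judgement.
- **Entry and on-study thresholds may differ on purpose.** Exclusion costs a subject no treatment or follow-up, whereas discontinuation does. This stands for discontinuation, and the fix leaves that decision open. It gives no reason to withhold an assessment or referral.
- **The rates are assumed.** Correct. They illustrate scale and carry no part of the conclusion.

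**Conclusion.** The concern holds. As written, 8.10 requires no action for on-study suicidal behavior with ideation below 3, although the same section and exclusion 17 treat behavior alone as disqualifying at entry. The provisions elsewhere reduce the risk but do not supply the two named steps.

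This rests on the text alone and does not depend on any event rate. The number affected is probably small, between about 0.3 and 2.6 of 255 subjects under the assumed rates of 0.1% to 1%. The consequence for one such subject could be grave, so the rule should be corrected.

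**What to change.** Amend 8.10 so that any suicidal behavior on study, whatever the ideation score, requires an investigator suicide risk assessment and psychiatric referral. Leave discontinuation on behavior alone to the clinical team. Keep the Follow-Up Visit within the trigger. No C-SSRS is scheduled at Week 14, so the wording should also cover behavior that comes to light outside a scheduled assessment. As a purely editorial matter, the same amendment can add Week 13 to the C-SSRS visit list in 8.10, with a matching edit in SAP 11.8, to agree with the schedules.

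The clinical change is one sentence and uses actions that 8.10 already names. It adds no C-SSRS administrations. It is still a protocol amendment: Protocol 13.7 requires the same review as the original protocol, including IRB approval, and SAP 6.5 reports 38 enrolling sites. The downside is possibly a few more risk assessments, referrals or withdrawals. SAP 6.5 describes site enrollment in the past tense. If enrollment has ended, the change helps only subjects still on treatment and later protocols that reuse this text, including the Phase 3 studies that SAP 3.1 anticipates.

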8.11 Additional Safety Measures

Subjects and caregivers will be instructed to inform the study physician and/or research personnel of any AEs that occur at any time during the study.

Procedures will be completed as specified in this protocol unless contraindicated due to a reported AE.

If, in the judgement of the Investigator, additional testing is required to assess an adverse event or otherwise clinically significant event, this testing should be discussed first with the sponsor unless needed urgently.

8.12 Cognitive Battery

At Screening, the Repeatable Battery for the Assessment of Neurological Status-Delayed Memory Index (RBANS DMI), Mini Mental State Exam (MMSE), Clinical Dementia Rating (CDR), and the Modified Hachinski Ischemia Scale (MHIS) will be used to assess the cognitive status of the subject.

During the Baseline Visit, the subjects will be reassessed on RBANS and MMSE. Caregivers will also complete the Alzheimer's Disease Cooperative Study Activities of Daily Living Inventory (ADCS-ADL).

The subjects will be assessed with the RBANS and MMSE instruments at Weeks 1, 2, 4, 8, and 13 during the treatment period. The investigator will also assess subjects using the CGI-I scale at Weeks 1, 2, 4, 8, and 13. Caregivers will be asked to complete the ADCS-ADL at Weeks 8 and 13.

[Section 16.3 Cognitive Test Scales](#) provides a summary description for each of the test in the cognitive battery to be assessed in this study.

8.13 Clinical Global Impression- Improvement

At the clinic visits during Weeks 1, 2, 4, 8, and 13, the Investigator will assess the degree of improvement in the subject with respect to their AD on a 1-7 point scale, where:

- 1=Very much improved
- 2= Much Improved
- 3= Minimally improved
- 4= No Change
- 5=Minimally worse
- 6= Much worse
- 7=Very much worse

8.14 Pharmacokinetic Assessment

8.14.1 Plasma Pharmacokinetic Samples

Blood samples for BPN14770 concentrations will be drawn during the clinic visits at Weeks 1, 4, 8 and 13. Samples will be drawn at the time of the clinic visit, with documentation of time of day testing was performed, and time of day of most recent dose of study medication.

Pharmacokinetic samples will be retained and may also be utilized subsequently for biomarker assessment. Blood samples (1 × 4 mL) will be collected in Vacutainer tubes containing K₂-EDTA as a preservative.

8.14.2 Processing and Shipment of Pharmacokinetic Samples

Blood samples will be kept on wet ice from the time of collection and throughout processing until frozen.

8.14.2.1 Pharmacokinetic Sampling

Blood samples will be centrifuged at approximately 3000 rpm for 10 minutes at 4°C. If a chilled centrifuge is not available, it is acceptable to keep sample on wet ice prior to centrifugation and use an ambient centrifuge to process the sample. The resulting plasma samples will be harvested and transferred into appropriately labeled polypropylene screw-cap tubes. Pharmacokinetic samples will be placed in a freezer at -70°C within 60 minutes of the blood draw. If a clinical site does not have a -70°C or -80°C freezer, it is acceptable to use a -20°C freezer, but samples stored must be shipped for storage with the laboratory vendor within 2 weeks of collection. Samples will remain frozen until assayed. A more detailed description of plasma sample preparation requirements may be provided by the analytical laboratory and will supersede those provided in this protocol. Appropriate documentation will be placed in the study master file at the Clinical Site.

The samples will be transferred to the central laboratory for storage after completion of the study or at mutually agreed upon time points during the clinical conduct of the study. Prior to shipment, the samples will be appropriately packed in a Styrofoam cooler containing dry ice. Sufficient dry ice will be added to ensure that the samples will remain frozen for at least 72 hours for remote shipments. The shipment will be accompanied by documentation containing the following information: name of the study drug product, protocol number, number of subjects, and number of samples included in the shipment.

All frozen pharmacokinetic samples will be shipped with accompanying documentation (Study ID BPN14770-CNS-201 / 38019XX045; Site Number: XXX) to:

Eurofins Central Laboratory Lancaster
Eurofins Central Laboratory, LLC.
[name]
[name]
[name]
United States of America
[contact]

The central lab will ship the PK samples to the analytical lab (CMIC, Inc., Hoffman Estates, IL) at mutually agreed upon time points during the study. PK samples will be stored in a freezer at -80°C both the central and analytical lab.

8.14.2.2 Metabolite Sampling at Week 13 (select sites)

At approximately 5-6 study sites, an additional sample of plasma spun for PK analysis will be aliquoted for assessment of BPN14770 metabolites at Week 13. Instructions for storing and shipping the plasma vials for metabolite assessment will be provided to the select participating sites.

8.14.3 Analytical Methods

Plasma samples for standard PK and metabolites will be analyzed for BPN14770 using validated assays.

Samples will only be analyzed for subjects whose treatment included administration of BPN14770. Samples will not be analyzed when matching placebo for BPN14770 was administered.

8.14.4 Plasma Pharmacokinetic Parameters

BPN14770 plasma concentration levels will be presented in tabular form by dose level and week, and a listing of all subjects' data will be provided. Metabolite data will be analyzed and reported separately from the clinical study data.

